Dosing for IN ketamine varies depending on the indication and generally based on the desired effect. Dosing for analgesia, a blend of both analgesia and mild sedation (analgesedation), and moderate-deep sedation varies, and is limited based on the volume delivered. The suggested range for pediatric analgesia is 0.5-3 mg/kg and pediatric PSA is 3-9 mg/kg [3, 10]. In a study using IN ketamine for laceration repair, 3 out of 4 (75%) patients achieved “adequate” sedation using dose of 9 mg/kg. Data safety monitoring committee stopped the study because there were too many failures at doses of 3

mg/kg and 6 mg/kg, suggesting that at 9 mg/kg PSA with IN ketamine alone could be a feasible and efficacious choice for painful procedures [3, 8, 13]. IV ketamine is a commonly employed and validated agent for pediatric PSA in the ED for myriad indications. This study explores the efficacy of IN ketamine as compared to IV ketamine for PSA for the closed reduction of isolated, non-operative fractures in the pediatric ED. We will secondarily compare the duration of sedation, adverse events, and ED length of stay (LOS) between the two groups.

References listed from above:

- 3. C. Fantacci, G. C. Fabrizio, P. Ferrara, F. Franceschi, A. Chiaretti**
Intranasal drug administration for procedural sedation in children admitted to pediatric Emergency Room
- 9. Quinn, Kellie (07/2018). "Analgesic Efficacy of Intranasal Ketamine Versus Intranasal Fentanyl for Moderate to Severe Pain in Children: A Prospective, Randomized, Double-Blind Study.". *Pediatric emergency care (0749-5161)*, p. 1.**
- 10. Rech, Megan A (08/2017). "When to Pick the Nose: Out-of-Hospital and Emergency Department Intranasal Administration of Medications.". *Annals of emergency medicine(0196-0644)*, 70 (2), p. 203.**

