dedicated automated medication dispensing system in the ED. These syringes will be pre-labelled by a color code without identifying the drug inside. Color code indicates the route of administration (Intranasal or Intravenous). Treatment allocated to the patient will only be known to the research pharmacist. Research pharmacist will maintain a log of randomization ID and patient identifier. Study drugs will be discarded at the conclusion of the sedation per our ED protocol. Sedating physician will document randomization ID in their sedation record. Study pharmacist will use pyxis data entry and documentation to verify drug administration and drug dosage.

Breaking the blinded code:

We do not anticipate any serious adverse events and need for premature code breaking. After all patients are enrolled and data entry is complete, we will break the blinded code just before data analysis.

Sedation induction and monitoring:

Subject randomized to the IN ketamine will receive IN Ketamine. After 8 minutes, IV Normal Saline (NS) will be given over 30 seconds. Subjects randomized to IV Ketamine will first receive IN hypertonic (3%) saline. After 8 minutes, IV Ketamine will be given over 20-30 seconds.

The study personnel will assess the level of sedation at 5-minute intervals, per our ED protocol, after IN medication administration (induction dose) using the modified Ramsay sedation scale until a score of ≥ 4 is achieved, which will serve as our definition of adequate sedation. Modified Ramsay Sedation scale scores range from 1-8 based on wakefulness of the patient. Score of 1 indicates fully awake and alert whereas score of 8 indicates unresponsive to external stimuli including pain. This scoring will be done by trained study personnel. Sedation scoring will be continued at 5-minute intervals until the reduction is completed. Failure of sedation will be defined as not achieving adequate sedation by Ramsay score of < 4 within 10 minutes of IN administration.

Patients who fail sedation at 10 minutes will receive 0.5 mg/kg IV ketamine or more, with additional IV doses as deemed necessary by treating physician. No subsequent IN medications will be given after the induction dose. Duration of successful sedation will be defined as induction dose time to when the patient is appropriate for discharge from sedation as noted by sedating ED physician. Discharge criteria includes patient said to have reached baseline/pre-sedation modified Aldrete Score.

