- c.** What is the total amount of time each participant will be involved? Participant will be involved until discharge from the ED. This is variable for each patient depending on the medical condition. On average, total time should be less than 6 hours accounting for the entire duration of ED stay.
- d.** If different phases are involved, what is the duration of each phase in which the participants will be involved? If no phases are involved, enter "None." None
- e.** List the procedures, the length of time the procedure takes, the total # of times the procedure is performed, and indicate whether each is performed solely for research or would already be performed for treatment or diagnostic purposes (routine care) for the population.
-Insert additional table rows as needed.
-If procedure is sometimes research and sometimes routine care, include on separate lines with number of times as each.

Procedure	Length of Time Required of Participants	Total # of Times the Procedure is Performed	Research (Res) –OR-Routine Care
Enrollment/Informed Consent	10-15minutes	Once	 Res  Routine
Sedation and Procedural consent	5 minutes	Once	 Res  Routine
Sedation induction (IV or IN Ketamine)	8 minutes	Once	 Res  Routine
Sedation induction		Once	 Res  Routine
Rescue medications	Over the length of reduction procedure	Repeated as needed	 Res  Routine
Reduction procedure	5-60 minutes	Once	 Res  Routine
Sedation monitoring	From induction dose to ED discharge	Once	 Res  Routine
Sedation monitoring	From induction dose to ED discharge	Once	 Res  Routine

- f.** Will an interview script or questionnaire be used? Yes No
If Yes, attach a copy.
- g.** Will participants incur any costs as a result of their participation? Yes No
If Yes, describe the reason for and amount of each foreseeable cost. _____
- h.** Will participants be compensated? Yes No

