If Yes, complete i-v.
 - i.** Type: (e.g., cash, check, gift card, merchandise): Greenphire Clincard

ii. Amount or Value: **\$10**

iii. Method (e.g., mail, at visit): **At visit**

iv. Timing of Payments: (e.g., every visit, each month): **only at the ED visit on day of enrollment. There will be no follow up visits.**

v. Maximum Amount of Compensation per Participant: **\$10**

18. Benefits

a. Describe the potential benefits of the research. **Study will lead to better insight into the potential IN ketamine provides for PSA to achieve successful fracture reductions obviating the need for IV access.**

19. Risks - in nontechnical, lay language

a. List the known risks for participants as a result of participation in the research. This should not include the minimal risk of loss of confidentiality. However, it should include any physical, psychological, social, economic, and/or legal risks. If there is a greater than minimal risk of loss of confidentiality describe why this is so. Do not list risks associated with the standard-of-care procedures.

NOTE: Risks included here should be included in the consent form or information sheet, as applicable.

There is a risk of compromising confidentiality and patient's personal health information.

Otherwise, study will not lead to any additional risks or discomforts other than the normal, standard risks and discomforts associated with procedure. Ketamine is associated with some well-known side effects and giving the study drug intranasal is not known to increase the risk or severity of side effects. There may also be risks that are unknown at this time. The known side effects of Ketamine are: Vomiting, Drooling, Allergic reaction, Agitation, Decreased oxygen levels.

b. Estimate the frequency, severity, and reversibility of each risk listed. **It is highly unlikely that the patients' health information and/or confidentiality will be compromised. We will put in place multiple safeguards (as detailed in section 23) to minimize any potential risk to the patients' health information and/or confidentiality.**

c. Is this a therapeutic study or intervention?

Yes No

If Yes, complete i.-iii.

i. Describe the standard of care in the setting where the research will be conducted: _____

ii. Describe any other alternative treatments or interventions: _____

iii. Describe any withholding of, delay in, or washout period for standard of care or alternative treatment that participants may be currently using: _____

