g. What language will the prospective participant and the legally authorized representative understand? They will not be expected to understand anything more than an 8th grade reading level.

h. What language will be used to obtain consent? English will be used. Strictly for purposes of convenience for the Emergency Department and Children's of Alabama Interpreter Services any non-english speaking caregivers will be excluded from the study.

i. If any potential participants will be, or will have been, in a stressful, painful, or drugged condition before or during the consent process, describe the precautions proposed to overcome the effect of the condition on the consent process. If not, enter "None." In such situations, the treating physician will stabilize patients before informed consent process. Additionally, the person obtaining consent we will allow enough time for patients to understand the study and ask questions than a patient who is otherwise normal before they will sign the consent form.

j. If any protocol-specific instruments will be used in the consenting process, such as supplemental handouts, videos, or websites, describe these here and provide a copy of each. If not, enter "None."
None

k. How long will participants have between the time they are told about the protocol and the time they must decide whether to enroll? If not 24 hours or more, describe the proposed time interval and why the 24-hour minimum is neither feasible nor practical. The patient's/parent/legal guardian will have approximately 10 minutes to decide whether to enroll. Due to the constraint of enrolling patients prior to them undergoing the reduction procedure in the ED, we cannot allow for a 24-hour time period to decide whether to enroll. Since enrolling will not affect the care the patient will receive a ten-minute window to decide about enrollment is sufficient.

22. Procedures to Protect Privacy

a. Describe how you will protect the privacy interest of the participants. Include how you will make sure others cannot overhear your conversation with potential participants and that individuals will not be publicly identified or embarrassed. All discussions will remain private between research personnel, the patient, and their guardian(s). Individuals will not be publically identified in any way and thus will not be subject to embarrassment.

23. Procedures to Maintain Confidentiality

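### Items 21.k and 19.a tell the IRB that enrolment does not affect care and adds no discomfort beyond the procedure's own; the protocol's procedures contradict both

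*Combined protocol and SAP*

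**What the plan says.** Item 21.k says that families "will have approximately 10 minutes to decide whether to enroll". It gives two separate reasons. The first is timing: enrolment has to come before the reduction in the emergency department, so "we cannot allow for a 24-hour time period to decide whether to enroll". The second supports the adequacy of the ten minutes: "Since enrolling will not affect the care the patient will receive a ten-minute window to decide about enrollment is sufficient".

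Item 19.a names loss of confidentiality and then says that otherwise the "study will not lead to any additional risks or discomforts other than the normal, standard risks and discomforts associated with procedure". It adds that "giving the study drug intranasal is not known to increase the risk or severity of side effects", allows that unknown risks may exist, and lists five known side effects of ketamine. The form's note to item 19.a says that risks entered there should also go into the consent form. Item 19.b asks for the frequency, severity and reversibility of each listed risk, and the answer deals with confidentiality only.

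Item 17.a describes the induction. On the IV arm: "Subjects randomized to IV Ketamine will first receive IN hypertonic (3%) saline. After 8 minutes, IV Ketamine will be given over 20-30 seconds". On the IN arm, ketamine goes in by the nose at time zero and the syringe given at 8 minutes is normal saline.

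**The concern.** The statement in 21.k is the only reason given for calling ten minutes enough, and it describes a study that leaves care unchanged. The protocol describes a blinded, double-dummy comparison of two routes, which by design changes how each enrolled child is sedated.

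Item 19.a has the same difficulty. Because it is meant to feed the consent form, a feature left out there may also be left out of what families read. At stake is whether the IRB judged the consent process on an accurate description of the study, and whether the risk list covers the steps that exist only because of the research. No estimate, test or sample size depends on this.

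**Working it through.** The plan gives no figure to reproduce on this point, so the check sets the two statements beside the procedures.

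**Does enrolment affect care (21.k)?**
- Route: item 17.a randomises children 1:1 to intranasal or intravenous ketamine. Item 15 says the IV route is the one most commonly used for sedating children. Enrolment therefore replaces a clinical choice of route with chance.
- Intranasal agent: items 16.e and 17.a give every child one, either ketamine or 3% saline. Planned numbers are 35 + 35 = 70 of 70 children, and the planned 35 on the IV arm receive saline only for blinding. Randomisation is simple, so the actual split may differ.
- Timing of the first ketamine dose, from item 17.a: IN arm at 0 minutes, IV arm at 8 minutes. The interval from the nasal dose is 8 − 0 = 8 minutes, and the sedation score at 5 minutes on the IV arm precedes any ketamine.
- IV ketamine on the IN arm: none at 8 minutes. It is given only as rescue, either for failure at the 10-minute assessment or if needed later in the procedure.
- The protocol's own label: in the item 17.e table, the row "Sedation induction (IV or IN Ketamine") is given a length of 8 minutes and ticked Research. The next row, headed simply as sedation induction, is ticked Routine. Induction as such is usual care, but the 8-minute form of it is research.
- Not counted: IV access, which item 17.a describes as the centre's existing practice.

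**Does the study add nothing beyond the procedure's own risks and discomforts (19.a)?** Items 19.a and 19.b do not mention the 3% saline, the 8-minute interval, or the possibility that the nasal dose will not sedate adequately. The last is foreseeable from item 15. At the IN dose used here it reports that "3 out of 4 (75%) patients achieved" adequate sedation, in a laceration-repair study stopped because too many children failed at lower IN doses. Item 15 also says that IN ketamine has not been compared with IV sedatives or studied for closed fracture reduction.

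**How much does 3 of 4 tell us?** One failure in 4 is 25%. The exact (Clopper-Pearson) 95% limits for the failure proportion p are:
- lower: 1 − (1 − p)^4 = 0.025, so p = 1 − 0.975^(1/4) = 0.006, or 0.6%;
- upper: (1 − p)^4 + 4p(1 − p)^3 = 0.025, so p = 0.806, or 80.6%.

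That evidence is compatible with almost any failure frequency. It supports saying that the frequency is very uncertain, and nothing more precise.

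**The case against.** The best defence is that these are answers on an IRB form, not statements to families. The consent form and the Drug Review Sheet are not in the reviewed text. Item 21.f says staff will keep strictly to the consent and assent forms, and those may well describe the randomisation, the nasal agent, the interval and rescue. This stands. A reader might infer that parents are misled or that consent is invalid for all 70 children; the documents do not show that.

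Several further points also stand:
- The 24-hour exception already rests on timing, and item 21.i promises stabilisation before consent and enough time for questions.
- Item 19.a is not a bare denial of risk. It names confidentiality, ketamine side effects and unknown risks, and item 20.a plans monitoring for unknown effects of the intranasal route.
- Item 19.a tells the investigator to leave out standard-of-care risks. Item 17.a says rescue doses are often needed, and item 17.e ticks rescue as both research and routine. Only an excess need for rescue with the nasal route would be a research risk, and the documents do not quantify one.
- The 8 minutes run from the nasal dose. No usual time to IV induction is given, so a reader who takes 8 minutes as the net delay against routine care goes beyond the text.
- Nothing in the documents says that 3% saline causes nasal discomfort.

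None of this removes the contradiction. Timing explains why 24 hours is impossible; the disputed clause is what is offered to show that ten minutes suffices. A general caveat about unknown risks does not disclose known features of the design.

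**Conclusion.** The concern holds as an internal inconsistency in the IRB form. The clause in 21.k is wrong on the protocol's own procedures, and the no-added-risk sentence in 19.a cannot stand beside items 16.e, 17.a and 17.e. The inconsistency covers all 70 planned children as regards random route and an intranasal agent, and the planned 35 on the IV arm as regards 3% saline and the 8-minute interval.

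It is tempting to apply 1 in 4 to the 35 IN-arm children and forecast about 9 failures (0.25 × 35 = 8.75). The documents do not support that forecast. The plan assumes no failure rate. The 3 of 4 comes from laceration repair, with no definition of adequate sedation given in item 15, whereas this trial counts a modified Ramsay score below 4 at 10 minutes or any rescue dose.

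The point deserves correction, but it is not of the highest severity: harm to the consent process is not shown while the consent form is unseen, and no statistical quantity changes. It would weigh more if the consent form repeated the same statements.

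**What to change.** - **21.k:** delete the clause saying that enrolment does not affect care, and rest the short window on the emergency department timing already stated there.
- **19.a:** reconcile with 16.e, 17.a and 17.e by listing the research-only features: route assigned by chance; intranasal ketamine or 3% saline for every child; the 8-minute interval before the IV syringe; and possible inadequate sedation by the IN route, with IV rescue as already described in 17.a.
- **19.b:** address the risks listed in 19.a, not confidentiality alone. State that the evidence cited in item 15 at this IN dose is 3 of 4 children in laceration repair, so the failure frequency is very uncertain. Give no projected count.
- **Consent form:** confirm that it matches the revised 19.a.

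The cost is an IRB wording amendment to three items and, if it does not already match, to the consent form. The risk statement will read less favourably, and a few more families may decline.
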